#### **5.3.4. Compliance**

Investigational product compliance will be assessed at each follow up clinic visit following. Any deviations in compliance should be recorded and an explanation provided. Study drug compliance is assessed using dosing compliance calculation:

% Compliance = number of tablets taken/number of tablets expected to have taken ×100.

The subject is non-compliant with dosing if the percentage compliance according to the above formula is less than 80% or greater than 120% study drug compliance.

If the subject has not been compliant with the dosing/administration regimen at a given visit, the subject's participation in the study should be re-evaluated. If the subject's compliance is outside this range, this will be recorded as a protocol deviation.

Compliance with daily pain and sleep diary completion will be assessed. Subjects must complete at least 4 daily pain and sleep diaries over each consecutive 7-day period in the study. The completion of fewer than 8 daily pain and sleep diaries over the course of 14 days will be recorded as a protocol deviation. If the subject has not been compliant with diary completion, the subject's participation in the study should be re-evaluated.

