### **7.2. Efficacy Assessments**

#### **7.2.1. Daily IVRS Diary**

The daily diary, comprising the daily pain NRS and the SIRS is to be completed daily by IVRS, every evening, from Visit 1 until study completion.

The daily diary assessments obtained via IVRS during the 7 days between Visit 1 and Visit 2 will be used to determine subject eligibility into the trial. A minimum of 4 days of daily diaries between Visits 1 and 2 must be completed for a subject to be considered compliant.

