#### **7.2.1.2. Secondary Efficacy Assessment: Sleep Interference Rating Scale (SIRS)**

The Daily Sleep Interference Rating Scale (SIRS) consists of an 11-point NRS ranging from 0 ("pain does not interfere with sleep") to 10 ("pain completely interferes with sleep" [unable to sleep due to pain]). Subjects describe how pain has interfered with their sleep during the past 24 hours:

Select the number that best describes how your neuropathic pain has interfered with your sleep during the past 24 hours on a scale from 0 to 10 where 0 represents 'does not interfere with sleep' and 10 represents 'completely interferes which means you are unable to sleep due to pain.'

Daily IVRS diaries will be completed by the subject from the evening of Visit 1/Screening through Termination.

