### **7.3.3. Sleep Score from the Daily Sleep Diary (NRS-Sleep)**

Pain-related sleep interference will be assessed on an 11-point numerical rating scale

(NRS Sleep) ranging from 0 (did not interfere with sleep) to 10 (completely interfered [unable to sleep due to pain]). Subjects are to describe how their pain has interfered with their sleep during the past 24 hours by choosing the appropriate number between 0 and 10. The NRS-Sleep is included in the subject electronic diary and self-assessment will be performed daily upon awakening from baseline to the end of the study.

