### **9.1.1. Analysis of Primary Endpoint**

- To evaluate efficacy, we will compare the endpoint mean pain score for the Lyrica group compared to the placebo group using an analysis of covariance (ANCOVA) model with treatment and center as main effects and the baseline PI score as a covariate.
- A BOCF and a modified or hybrid approach (mBOCF) will be used to account for missing data at last treatment Week. As a sensitivity we will look at the LOCF, MMRM and the missing imputation (suggested the National Academy of Sciences report).

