### **9.1.2. Analysis of Secondary Endpoints**

Secondary analyses included examination of the PGIC and sleep interference rate will be compared between treatment groups using a Cochran-Mantel-Haenszel test.

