- d V6 is the final visit of the single-blind phase and also the randomization visit for subjects who are eligible to continue in the withdrawal phase.
- e Includes weight, blood pressure, and pulse at all clinic visits, and height at Visit 1 only.
- f Rescue medications may NOT be taken within the 2 hours prior to daily diary completion

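### The sleep-interference comparison in Section 9.1.2 is not fully defined and makes no stated use of the baseline sleep score that the diary already collects

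*Combined protocol and SAP*

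**What the plan says.** SIRS is a listed secondary endpoint (Section 2.2). Its whole analysis plan is the statement in Section 9.1.2 that "sleep interference rate will be compared between treatment groups using a Cochran-Mantel-Haenszel test", in a sentence it shares with the PGIC. No analysis week, scoring, responder cut-point, stratification factor or baseline value is given there or elsewhere.

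The measure is described in Section 7.2.1.2: "The Daily Sleep Interference Rating Scale (SIRS) consists of an 11-point NRS ranging from 0", running up to 10. It is collected with pain: "The daily diary, comprising the daily pain NRS and the SIRS is to be completed daily by IVRS" (Section 7.2.1). The collection period is also stated: "Daily IVRS diaries will be completed by the subject from the evening of Visit 1/Screening through Termination" (Section 7.2.1.2). Section 5.3.4 sets the minimum density: "Subjects must complete at least 4 daily pain and sleep diaries over each consecutive 7-day period in the study". Randomisation comes at the end of the 8-week single-blind phase, since "V6 is the final visit of the single-blind phase and also the randomization visit" (Appendix 1, footnote d).

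For pain, scored 0-10 in the same diary, Section 9.1.1 specifies an "analysis of covariance (ANCOVA) model with treatment and center as main effects and the baseline PI score as a covariate".

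On timing, Section 7.2.1 has the diary that contains SIRS filled in each evening. Section 7.3.3 describes a sleep-interference item on the same 0-10 scale for which "self-assessment will be performed daily upon awakening from baseline to the end of the study".

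**The concern.** Two scales of the same form, recorded in the same diary over the same period, are analysed differently, and the protocol gives no reason. Every randomised patient should have a weekly mean SIRS from just before randomisation, yet nothing in the plan puts it into the sleep comparison.

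Three things are at stake, all on a secondary endpoint:

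- **Precision.** If the pre-randomisation sleep score predicts the final one, adjusting for it removes variance at almost no cost. With 20 patients per arm planned, there is little precision to spare.
- **Interpretation.** A Cochran-Mantel-Haenszel test delivers a p-value, not a treatment difference in points on the 0-10 scale.
- **Pre-specification.** Because the rate is undefined, a mean-score test, a test of a dichotomised score and tests with different strata all fit the sentence. The choice among them would be open after the data are seen.

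**Working it through.** **The plan's own figure.** Section 9.1 gives no calculation for sleep. For pain it states a difference of 1.1, SD 2, alpha 0.05, 90% power and 20 per group. The usual two-sample formula does not return 20: n = 2 × (1.960 + 1.282)² × 2² / 1.1² ≈ 69.5, so 70 per arm two-sided (57 one-sided). That is a separate problem with the primary endpoint, and the sleep point does not depend on it.

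**Inputs for sleep.** From Section 9.1: 20 per arm. Assumed, because the documents give nothing for SIRS: difference 1.1 and SD 2 (borrowed from pain), two-sided 0.05 (Section 9.1 does not state sidedness), and a range for ρ, the correlation between baseline and final weekly SIRS.

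**Formula.** Adjusting for baseline leaves a residual SD of 2 × √(1 − ρ²). The noncentrality is 1.1 / (residual SD × √(2/20)). Power comes from the noncentral t distribution with 38 degrees of freedom; using 37, to allow for the covariate, changes it by less than 0.1 percentage point.

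Without adjustment: 1.1 / (2 × 0.3162) = 1.739, power 39.6%. At ρ = 0.5: residual SD 1.732, noncentrality 2.008, power 49.9%.

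| ρ | Variance left (1 − ρ²) | Residual SD | Power by formula | Simulated ANCOVA |
|---|---|---|---|---|
| 0 | 1.00 | 2.000 | 40% | 38% |
| 0.3 | 0.91 | 1.908 | 43% | 41% |
| 0.5 | 0.75 | 1.732 | 50% | 48% |
| 0.6 | 0.64 | 1.600 | 56% | 53% |
| 0.7 | 0.51 | 1.428 | 66% | 61% |
| 0.8 | 0.36 | 1.200 | 81% | 75% |

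**Simulation of the tests themselves.** The last column comes from 8,000 simulated trials per ρ, with 20 per arm and scores rounded to integers and limited to 0-10. On the same data:

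- The mean-score Cochran-Mantel-Haenszel test without strata had about 38-39% power at every ρ.
- The same test on a dichotomised score (4 or more, an assumed cut) had about 27%.
- A Cochran-Mantel-Haenszel test stratified at the baseline median had 43% at ρ = 0.5 and 50% at ρ = 0.7, so it recovers only part of the gain.

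**How firm the absolute powers are.** Section 9.1 words the difference as one from baseline, so the SD of 2 may belong to a change score. With equal variances at both times, the SD of a single score is then 2 / √(2(1 − ρ)). At ρ = 0.7 that is 2.582, and power goes from 26% unadjusted to 45% adjusted, rather than from 40% to 66%. The variance ratio of 0.51 is the same either way.

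**The case against.** The strongest case for leaving the plan alone has four parts.

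**The test is valid.** A reader might infer that a categorical test on a 0-10 score is wrong in itself, or that chance baseline imbalance biases it. Neither follows. Under randomisation the Cochran-Mantel-Haenszel test keeps its type I error, and that error rate already allows for chance imbalance. Imbalance is therefore not a second harm on top of lost precision. This objection stands in full.

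**The plan never says the test is unadjusted.** The procedure is built for strata, and Section 9.1.1 already uses center as a factor, so a center-stratified test may be intended. What the documents support is that no strata are named. Even a center-stratified test would bring in no baseline sleep value.

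**The word rate may be deliberate.** It could be a slip for rating, or it could mean a responder proportion. If the latter, the test is conventional and the defect is the missing cut-point. The documents do not settle which. Either way the endpoint is not defined, and a dichotomised score would lose further power.

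**The size of the loss is unknown.** This is right. A reader might infer that much of the available precision is being given up, but no document gives a correlation for SIRS. At ρ = 0.2 the formula gives only 41% against 40%.

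ANCOVA on a bounded score with 20 per arm also carries assumptions that a table-score test avoids. In the simulation on bounded integer scores it matched the unstratified test at ρ = 0 (38% against 39%) and beat it at every higher ρ tried.

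**Conclusion.** The point holds as one of lost precision, a missing effect estimate and an endpoint left undefined. It does not hold as a claim that the test is invalid, that it is certainly unadjusted, or that sleep cannot be analysed as a proportion.

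With the pain figures as a stand-in, adjustment adds about 3 percentage points of power at ρ = 0.3, 10 at 0.5 and 26 at 0.7 by formula. In the simulation it adds roughly 2 to 3, 8 to 10 and 22 to 23 over the unstratified test. The gain is small at low correlation and substantial at 0.6 or above. Only the variance ratio 1 − ρ² is free of the borrowed difference and SD, and ρ itself is an assumption. Since the baseline data are already collected, adjusting is an essentially free improvement. The argument concerns sleep only: the PGIC is itself a rating of change on 7 categories, and the Cochran-Mantel-Haenszel test suits it.

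**What to change.** In Section 9.1.2:

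1. Define the sleep endpoint as the mean SIRS over the last week of the withdrawal phase.
2. Analyse it by ANCOVA with treatment and center as effects and, as covariate, the mean SIRS over the last single-blind week before Visit 6.
3. Name that week as the sleep baseline, including for any carry-forward of missing data. This needs saying because Section 9.1.1 does not define its baseline, and Appendix 1 (footnote c) attaches the term single-blind baseline to Visit 2.
4. Report the adjusted difference with a 95% CI.
5. Keep the Cochran-Mantel-Haenszel test for the PGIC, and name its strata if there are any.

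Separately, Sections 7.2.1 (evening) and 7.3.3 (on awakening) must be reconciled on when the sleep item is completed, so that the weekly mean is well defined.

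The cost is a few sentences of text and one degree of freedom for the covariate. No new data are needed.

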## **9.2. Safety Analysis**

Safety data will be presented separately for both single-blind and double-blind phases of the study. Safety data will be tabulated and listed according to Pfizer's standard reporting algorithms.

## **10. QUALITY CONTROL AND QUALITY ASSURANCE**

The study site may be subject to review by the Institutional Review Board (IRB). It is important that the investigator(s) and their relevant personnel are available during the monitoring visits and possible audits or inspections and that sufficient time is devoted to the process.

## **11. DATA HANDLING AND RECORD KEEPING**

### **11.1. Case Report Forms/Electronic Data Record**

As used in this protocol, the term CRF should be understood to refer to either a paper form or an electronic data record or both, depending on the data collection method used in this study.

A CRF is required and should be completed for each included subject. The investigator has ultimate responsibility for the collection and reporting of all clinical, safety and laboratory data entered on the CRFs and any other data collection forms (source documents) and ensuring that they are accurate, authentic / original, attributable, complete, consistent, legible, timely (contemporaneous), enduring and available when required. The CRFs must be signed by the investigator or by an authorized staff member to attest that the data contained on the CRFs is true. Any corrections to entries made in the CRFs, source documents must be dated, initialed and explained (if necessary) and should not obscure the original entry.

In most cases, the source documents are the hospital's or the physician's subject chart. In these cases data collected on the CRFs must match the data in those charts.

## **11.2. Record Retention**

To enable evaluations and/or audits from regulatory authorities, the investigator agrees to keep records, including the identity of all participating subjects (sufficient information to link records, eg, CRFs and hospital records), all original signed informed consent documents, copies of all CRFs, safety reporting forms, source documents, and detailed records of treatment disposition, and adequate documentation of relevant correspondence (eg, letters, telephone calls reports). The records should be retained by the investigator according to International Conference on Harmonization (ICH), local regulations, or as specified in the Clinical Study Agreement (CSA), whichever is longer.

## **12. ETHICS**

### **12.1. Institutional Review Board (IRB)**

It is the responsibility of the investigator to have prospective approval of the study protocol, protocol amendments, informed consent documents, and other relevant documents, eg, recruitment advertisements, if applicable, from the IRB. All correspondence with the IRB should be retained in the Investigator File.

The only circumstance in which an amendment may be initiated prior to IRB approval is where the change is necessary to eliminate apparent immediate hazards to the subjects. In that event, the investigator must notify the IRB in writing immediately after the implementation.

### **12.2. Ethical Conduct of the Study**

The study will be conducted in accordance with legal and regulatory requirements, as well as the general principles set forth in the International Ethical Guidelines for Biomedical Research Involving Human Subjects (Council for International Organizations of Medical Sciences 2002), Guidelines for GCP (ICH 1996), and the Declaration of Helsinki (World Medical Association 2008).

In addition, the study will be conducted in accordance with the protocol, the ICH guideline on GCP, and applicable local regulatory requirements and laws.

### **12.3. Subject Information and Consent**

All parties will ensure protection of subject personal data and will not include subject names on any sponsor forms, reports, publications, or in any other disclosures, except where required by laws.

Subject names, address, birth date and other identifiable data will be replaced by a numerical code consisting of a numbering system in order to de-identify the trial subject

The informed consent document must be in compliance with ICH GCP, local regulatory requirements, and legal requirements.

The informed consent document used in this study, and any changes made during the course of the study, must be prospectively approved by the IRB before use.

The investigator must ensure that each study subject, or his/her legal representative, is fully informed about the nature and objectives of the study and possible risks associated with participation.

The investigator, or a person designated by the investigator, will obtain written informed consent from each subject or the subject's legal representative before any study-specific activity is performed. The investigator will retain the original of each subject's signed consent document.

### **13. DEFINITION OF END OF TRIAL**

End of Trial is defined as the time at which it is deemed that sufficient subjects have been recruited and completed the study as stated in the protocol.

### **14. SPONSOR DISCONTINUATION CRITERIA**

Premature termination of this study may occur because of a regulatory authority decision, change in opinion of the IRB, drug safety problems, or at the discretion of Pfizer.

If a study is prematurely terminated or discontinued, the investigator must contact all participating subjects and the hospital pharmacy (if applicable) within 2 weeks. All study materials must be collected and all CRFs completed to the greatest extent possible.

### **15. PUBLICATION OF STUDY RESULTS**

Results will be publicly disclose through posting the results of this study on [www.clinicaltrials.gov](http://www.clinicaltrials.gov) (ClinicalTrials.gov).

For all publications relating to the Study, investigator will comply with recognized ethical standards concerning publications and authorship, including Section II - "Ethical Considerations in the Conduct and Reporting of Research" of the Uniform Requirements for Manuscripts Submitted to Biomedical Journals, <http://www.icmje.org/index.html#authorship>, established by the International Committee of Medical Journal Editors.

## APPENDIX 1. SCHEDULE OF ACTIVITIES

The Schedule of Activities table provides an overview of the protocol visits and procedures. Refer to Study Procedures and Assessments for detailed information on each procedure and assessment required for compliance with the protocol.

Study Phase:	Baseline (V1 to V2)	Single-Blind Treatment Phase (8 weeks)						Randomized Withdrawal Phase (4 weeks)
		V1 a,c	V2 a,c	V3	V4	V5	V6	
Clinic Visit No.:	V1 a,c	V1 a,c	V2 a,c	V3	V4	V5	V6	V7
Visit:	Screening	Enrollment	Wk 1	Wk2	Wk 4	Wk 8		Wk 12
Study Day:	-30 to -14	0	7	14	28	56		84
Visit Type:	Clinic	Clinic	Phone	Phone	Phone	Clinic		Clinic
Visit Window:	N/A	7 - 21 days	±2 days	±2 days	±2 days	±3 days		±3 days
Observation/Procedure								
Informed consent b	X							
Inclusion/Exclusion	X	X						
Medical History	X							
Physical exam/Neurological exam	X							X
Vital Signs e	X	X						X
Clinical labs	X							
Retained blood sample for proteomics, etc.	X							
IENF biopsy	X							
PainDETECT	X							
PHQ-8	X							
Suicidality Assessment (C-SSRS)	X	X					X	X
Adverse Events	X	X	X	X	X	X		X
Concomitant/Rescue medications f	X	X	X	X	X	X		X
Study medication dispensing		X				X		X
NPSI		X				X		X

Study Phase:	Baseline (V1 to V2)	Single-Blind Treatment Phase (8 weeks)					Randomized Withdrawal Phase (4 weeks)
SFN-SIQ		X				X	X
Numeric Rating Scale for Pain (NRS-Pain - 1 week recall)	X						
IVRS Daily Diary, (Pain NRS and SIRS)	X	X	X	X	X	X	X
Brief Pain Inventory - short form (BPI- sf)	X	X				X	X
EuroQOL 5-Dimensions (EQ-5D)		X				X	X
Patient Global Impression of Change (PGIC)						X	X

- a Visit 1 may occur between 30 days and 14 days prior to Visit 2, based on the amount of time required for screening procedures such as punch biopsy or washout period for previous pain medications. The screening visit may also be split into two visits. A 14-day minimum baseline between Visit 1 and Visit 2 is required to establish baseline pain level. The maximum 30-day screening period does not include prior completion of the informed consent.
- b Informed consent must be completed prior to performing any other study procedures, including any medication changes made to participate in the study. Any such medication changes must be considered for medical appropriateness to protect patient well-being.
- c V2 is the Single-blind Baseline visit (enrollment).
- d V6 is the final visit of the single-blind phase and also the randomization visit for subjects who are eligible to continue in the withdrawal phase.
- e Includes weight, blood pressure, and pulse at all clinic visits, and height at Visit 1 only.
- f Rescue medications may NOT be taken within the 2 hours prior to daily diary completion

## APPENDIX 2. Dose Assessment and Adjustment

Visit	Days	Response/Assessment	Action	Bottle
V2	0-7	--	Start 150 mg/day pregabalin/placebo (75 mg BID):	Bottle A
V3	7-14	Subject tolerates 150 mg/day well	Increase dose to 300 mg/day pregabalin/placebo (150 mg BID)	Bottle B
		In investigator's judgement, Remain at 150 mg/day pregabalin/placebo dose should not be increased based tolerability (ie, subject has pregabalin associated adverse events that clinically preclude dose increase		Continue with Bottle A
V4	14-28	Subject tolerates 300 mg/day well	If at 300 mg/day pregabalin/placebo, increase dose to 450 mg/day.	If at Bottle B, proceed to Bottle C
		Subject tolerates 150 mg/day	If still at 150 mg/day pregabalin/placebo, increase dose to 300 mg/day.	If at Bottle A, proceed to Bottle B
		In investigator's judgement, Remain at current dose pregabalin/placebo dose should not be increased based tolerability (ie, subject has pregabalin associated adverse events that clinically precludes dose increase		Maintain current bottle and dosing
		Not acceptable tolerability while receiving 300 mg/day	Reduce to 150 mg/day pregabalin/placebo.	Return to Bottle A
V5	28	Acceptable tolerability	Remain at current dose level; no further changes.	Maintain current bottle and dosing
		Not acceptable while receiving current dose	Reduce dose 1 level	
V6		Acceptable tolerability	Remain at current dose level; no further changes	Maintain current bottle and dosing
		Not acceptable while receiving current dose	Reduce dose 1 level	

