## **2. STUDY OBJECTIVES AND ENDPOINTS**

### **2.1. Objectives**

#### **Primary Objective:**

To evaluate the efficacy of pregabalin (150-600 mg/day, flexibly administered BID) compared with placebo for the treatment of pain associated with idiopathic distal symmetrical small fiber peripheral neuropathy.

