### 3. STUDY DESIGN

This enriched enrollment randomized withdrawal study comprises 4 phases: a screening and selection phase, a 2-4 weeks washout period from previous pain medication for enriched enrollment, an 8 week single-blind pregabalin treatment phase; and a 4 week randomized withdrawal phase. Patients who show any increase in their pain intensity score during the washout phase will be eligible for the single blind pregabalin treatment phase. Patients who respond to pregabalin, with at least 1 point improvement in neuropathic pain from baseline at the end of the single-blind pregabalin treatment phase and meeting all other study requirements are considered eligible for participation in the withdrawal phase. These eligible patients are randomly assigned (1:1) to continue pregabalin or to be switched to placebo for a comparison of pregabalin efficacy and safety. Patients who have a worsening of average pain relative to the last week of the single blind pregabalin treatment period by more than one point and average pain level  $\geq 4$  will be considered to have a loss of therapeutic response (LTR).

\*Low creatinine clearance patients: 150-300 mg/day

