### **5. STUDY TREATMENTS**

During the screening phase, the medication history of the subjects who are eligible for the study based on meeting the inclusion and exclusion criteria will be reviewed. The current pain medications of the subjects will be categorized into allowed and disallowed medications (see sections 5.3.7 and 5.3.8 for a complete list of these medications). If patient is on any of the

disallowed neuropathic pain medication such as gabapentin, these medications will be discontinued during the washout phase. A written instruction will be provided to the patient on how to discontinue the medication during the washout phase. Patient will complete a daily pain diary during this phase. Patient can continue to take the allowed pain medications but no change in dose or frequency is permitted. At the end of the washout period which is at least 14 days and might be longer based on the type of medication being discontinued, patient will be evaluated for eligibility for the study again based on randomization criteria mentioned in section 4.3.

All patients entering the study will be treated with single-blind pregabalin at doses of 150-600 mg/day for 8 weeks. The first 4 weeks of the single-blind phase comprise the dose optimization phase, and the next 4 weeks the single blind maintenance phase.

During the initial week of the single-blind pregabalin treatment phase, all patients will be treated with pregabalin 150 mg/day, and dose is to be increased based on response and tolerability until the end of Week 4. If the patient is unable to tolerate the higher dose, the dose should be reduced by one dose level per investigator discretion. This dose reduction may occur outside of the scheduled visit. Patients unable to tolerate a dose of 150 mg/day pregabalin during the Single-Blind phase will discontinue from the study (no taper necessary). After the end of the 4th week of the Single-Blind phase, no further dose escalation is permitted. During the next 4 weeks of the Single-Blind phase, fixed dose pregabalin treatment at the optimized dose within the range of 150 to 600 mg/day administered BID will be provided. One additional dose reduction may occur if needed during the last 4 weeks of the single blind period. Patients unable to tolerate the fixed dose of study medication will be discontinued from the study.

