Patients meeting all eligibility criteria for withdrawal phase will be randomized in a 1:1 fashion to continue the fixed dose of pregabalin treatment as they were taking in the Single-Blind phase or placebo. Patients will continue in the withdrawal portion of the study for 4 weeks.

Patients who discontinue from the study during or at the end of the single-blind pregabalin treatment phase will complete a taper. Patients who had been receiving pregabalin 450 or 600 mg/day will receive pregabalin 300 mg/day for 4 days and 150 for 3 days. Patients receiving pregabalin 150 or 300 mg/day will receive 150 mg/day for 4 days and 50 mg for 3 days. Patients who have not taken study medication for the past 24 hours or more are not required to receive the taper medication.

At the end of the single-blind pregabalin treatment phase, patients will be randomized to receive either pregabalin at the optimized dose (150-600 mg/day pregabalin), as determined during the treatment phase, or matching placebo. No further dose adjustments will be allowed.

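### Appendix 2 contains no titration step to 600 mg/day, although the primary objective, Section 5 and Appendix 3 all include that dose; the dosing passages must be reconciled

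*Combined protocol and SAP*

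**What the plan says.** **Range.** The primary objective (Section 2.1) is "To evaluate the efficacy of pregabalin (150-600 mg/day, flexibly administered BID) compared with placebo". Section 5 says "All patients entering the study will be treated with single-blind pregabalin at doses of 150-600 mg/day for 8 weeks", and at the end of that phase it randomises patients to "pregabalin at the optimized dose (150-600 mg/day pregabalin), as determined during the treatment phase, or matching placebo". Its taper rules, both for patients who stop and for those allocated to placebo, have an upper group that includes 600 mg/day. Appendix 3 has separate taper rows for 150, 300, 450 and 600 mg.

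**Escalation in the body text.** Section 5 starts everyone at 150 mg/day, and then "dose is to be increased based on response and tolerability until the end of Week 4". After the fourth "week of the Single-Blind phase, no further dose escalation is permitted". It does not set the size of an upward step. Section 5.3.3 permits dose adjustment by telephone. Section 6.2.4 (Visit 5, Day 28) has the investigator determine the dose level at that visit.

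**Escalation in Appendix 2.** Patients start at 150 mg/day at Visit 2 (Bottle A) and may go to 300 mg/day at Visit 3 (Bottle B). The highest step comes at Visit 4: "If at 300 mg/day pregabalin/placebo, increase dose to 450 mg/day" (Bottle C). At Visits 5 and 6 a patient with acceptable tolerability is to "Remain at current dose level; no further changes"; otherwise the dose goes down one level.

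**The concern.** Appendix 2 is the only place that sets out which dose follows which, at what visit and from which bottle. If it is followed as printed, no patient reaches the upper limit named in the primary objective. An efficacy or safety statement for 150-600 mg/day would then include a level that nobody received.

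If staff work from Section 5 or Section 6.2.4 instead, a further increase by Day 28 could be read as permitted. Two patients with the same response and tolerability could then enter the randomised phase on different doses, depending on the page consulted. Section 5 allows no adjustment after randomisation, so the difference would persist.

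**Working it through.** **1. Doses reachable under Appendix 2.** Following every permitted move, row by row (mg/day):

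| Visit | Moves allowed | Doses reachable |
|---|---|---|
| V2, Days 0-7 | start at 150 | 150 |
| V3, Days 7-14 | stay, or 150 to 300 | 150, 300 |
| V4, Days 14-28 | stay, 150 to 300, 300 to 450, or 300 back to 150 | 150, 300, 450 |
| V5, Day 28 | stay, or down one level | 150, 300, 450 |
| V6 | stay, or down one level | 150, 300, 450 |

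The maximum is 450 mg/day. The stated upper limit of 600 mg/day is not reproduced.

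**2. Number of increases needed.** The levels are 150 mg/day apart, so going from 150 to 600 takes (600 − 150) / 150 = 3 increases. Appendix 2 offers two, at V3 and V4: 150 + 2 × 150 = 450. A third increase at V5 would give 150 + 3 × 150 = 600, but the V5 row rules it out.

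**3. Supplied capsules.** Section 5.3.1 lists strengths of 75, 150, 225 and 300 mg, and Section 5.3.3 specifies one capsule twice daily. The daily doses are 2 × 75 = 150, 2 × 150 = 300, 2 × 225 = 450 and 2 × 300 = 600 mg. These are the four levels of Appendix 3. The 300 mg capsule corresponds to no titration level and no bottle in Appendix 2.

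**4. Whether other text supplies the missing step.**

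- Section 5 allows increases to the end of Week 4 but names no levels or visits for them.
- Section 5.3.3 says how an adjustment may be communicated, not which adjustment is allowed.
- Section 6.2.4 leaves the dose level open at Day 28, while the V5 row of Appendix 2 closes it to any increase on the same day. These two conflict directly.
- No contact is scheduled between Day 14 (Visit 4) and Day 28 (Visit 5).
- Visits 3 to 5 are by default telephone visits, and their sections describe no dispensing. Section 6 describes dispensing of study drug at Visits 2 and 6. The bottles a patient can move between would therefore ordinarily be in hand from Visit 2, and the only bottle list ends at C.
- After Week 4 Section 5 bars escalation, and after randomisation it bars any adjustment, so no later step can add the level.

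**5. Effect on the randomised contrast.** Under Section 5 the dose is optimised first. Patients are then allocated 1:1 to that dose or to placebo. The ambiguity acts before allocation and so applies equally to both arms. Sections 9.1.1 and 9.1.2 contain no analysis by dose.

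**The case against.** The best reply is that the range is flexible. The objective describes an individually optimised dose between two limits, and 150, 300 and 450 mg/day all lie within them. There is no dose-response objective or dose-specific endpoint. This stands as a limit on the point: only the top level is missing. A reader might infer that the trial fails to test its stated regimen at all, and the documents do not support that. A flexible range need not have anyone at its maximum; the narrower difficulty is that under Appendix 2 nobody can get there.

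A second reply is that Appendix 2 need not govern. Neither Section 5 nor the visit sections refer to it, and the tapers, capsules and Appendix 3 all expect patients on 600 mg/day. This also stands, and it means the plan cannot be read as excluding that dose. It is a conflict between passages, and the reply confirms the conflict without resolving it.

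Two further inferences should be avoided. One is that different sites would dose differently. Sections 5.3.2 and 10 read as a single site, and only the centre term in the Section 9.1.1 model suggests more; the ambiguity exists between staff at one site in any case. The other is that the note in Section 3, "Low creatinine clearance patients: 150-300 mg/day", is further evidence. It carries an asterisk with no visible anchor and may belong to a figure that is not shown. It does not say what counts as low, and Exclusion 16 already restricts entry by creatinine clearance. It does not bear on 450 against 600 mg/day.

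**Conclusion.** The contradiction is real and should be corrected. The only detailed titration schedule stops at 450 mg/day, while the primary objective, Section 5, the tapers, the capsule supply and Appendix 3 extend to 600 mg/day. Three of four levels are reachable under Appendix 2. Its Visit 5 row also conflicts with Section 6.2.4 on whether the dose is still open at Day 28.

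A reader might infer that the treatment comparison is biased. It is not, because the dose is fixed before allocation and both arms are drawn from the same optimised patients. Nothing here shows an effect on type I error or power. The consequences are inconsistent dosing instructions and a result whose dose range is not clearly defined.

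This rests on two assumptions: that Appendix 2 is followed exactly where it is used, and that its table is complete. Some cells are merged in the extracted text, but the rows from Visit 2 to Visit 6 appear whole and nothing suggests a lost row leading to 600 mg/day.

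**What to change.** Reconcile Section 2.1, Section 5 (dose range, escalation window and tapers), Section 6.2.4, Appendix 2 and Appendix 3. One dose range, one set of escalation steps tied to named visits, and one bottle list should appear throughout. State explicitly whether the dose may still rise at Day 28, and make the primary objective agree with the reconciled schedule. Which range and steps are kept is a clinical decision for the sponsor and investigator, and the documents do not settle it.

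The cost is a protocol amendment and a corrected dosing table, with no extra patients or analyses. If the upper level is kept, a further escalation step and bottle must also be fitted into the visit and supply plan, which is more than a change of wording. If it is not kept, the objective, Section 5, the taper rules and Appendix 3 all need matching edits.
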